[¥]The baseline high resolution, contrast-enhanced CT scan (2mm or less slice spacing) performed within three months prior to enrollment will be reviewed by the independent core lab for patient eligibility determination. Evaluations of endograft performance, renal stent graft patency and integrity, and stent graft patency and integrity will be made based upon post-operative CT scan evaluations by the core laboratory.

*Follow-up windows are ±2 weeks (1 month visit); ±1 month (6 month visit); ±2 months (Year 1 visit); ±3 months (Years 2 through 5 visits)

Statistical

Considerations: *Study Population:* The intent to treat (ITT) population in this study consists of all patients who are enrolled and treated.

Trial Success, Safety: The primary safety analysis is **Major Adverse Events (MAE)**, as previously defined. This analysis is limited to patients enrolled in the Trial Phase (i.e., roll-in patients are not included and will be reported as a separate feasibility group). The primary endpoint is to show that the % of patients with an MAE is statistically superior to that in the Endologix open surgical historical control group at 30 days. The hypothesis test will be evaluated by the exact test as a one-tailed test, using significance level $\alpha=0.025$. Multivariable analyses will be used to assess predictors of trial success.

Trial Success, Effectiveness: The primary effectiveness analysis is **Treatment Success**, as previously defined. This analysis is limited to patients enrolled in the Trial Phase (i.e., roll-in patients are not included and will be reported as a separate feasibility group). The primary endpoint is to show that the % of patients with Treatment Success is statistically superior to the target rate of 80% at one year. The hypothesis test will be evaluated using the exact binomial distribution as a one-tailed test, using significance level $\alpha=0.05$. Multivariable analyses will be used to assess predictors of trial success.

Additional Evaluations: Appropriate statistical methodology will be used to analyze all additional evaluations.

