4.3. TRIAL DESIGN

This is a multicenter, prospective, single arm clinical trial. Patients with JAA/PAA who are suitable candidates for endovascular repair using the Endologix Fenestrated Stent Graft System will be considered for enrollment.

After this protocol and the patient informed consent form are reviewed and approved by the local Ethics Committee or responsible Institutional Review Board, potential patients will be offered participation in the study. This will be accomplished through the patient's reading of the informed consent form in the patient's native language and discussion of the study with the patient by the investigator and site personnel. Agreement to participate and to attend all follow-up visits will be documented with the patient's signature on the informed consent form, with appropriate signatures of the site investigator and an impartial witness.

After providing written informed consent, screening and eligibility determinations will be performed. Patients will undergo a high resolution, contrast-enhanced computed tomography angiography (CT) scan of the relevant aortic and aortoiliac vasculature within three months of the scheduled procedure. Evaluation of the aortic and vascular anatomy suitability per this protocol, as depicted on the CT scan, will be performed by the site investigator and by an independent core laboratory. Other tests include a physical examination, review of patient medical history for exclusionary conditions, selected blood chemistry and hematology analyses, and ankle-brachial index determination.

Upon acceptance for enrollment, patients will be scheduled for the endovascular repair procedure.

Note: An investigational site may not enroll more than 20% of the total Trial Phase enrollment.

Following patient discharge from the hospital, the first follow-up visit will be made at one month (± 2 weeks). A CT scan will be performed to assess aneurysm morphology and device integrity and patency, as well as the status of the renal arteries and implanted stent grafts. Subsequent follow-up will be made at six months, one year, and annually to five years.

Continued patient follow-up beyond five years is outside of the scope of this study. Nonetheless, all patients should be monitored and evaluated per the institutional standards of care for patients who receive an endovascular stent graft.

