5. STUDY POPULATION

5.1. NUMBER OF PATIENTS

Up to 25 sites and up to 122 patients will participate in this trial. Following investigator training, each investigator will treat one patient during a roll-in phase. These (maximum 25) patients will not count toward the Trial Phase cohort. Note that the Roll-In phase requirement may be waived at the discretion of Endologix for a site that participated in the Pilot Study or Feasibility Study of this same device system.

During the Trial Phase, 97 patients are planned to be enrolled at the investigational sites. In both phases, screening results, including the independent core laboratory evaluation of the pre-operative CT scan, will be used to make a final determination as to patient suitability for enrollment. Patients must meet **all** inclusion criteria and **no** exclusion criteria in order to participate.

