10.6.2 Sample Size

The primary trial safety variable is the rate of MAEs (as previously defined) at 30 days following treatment with the Fenestrated Stent Graft System. In the U.S., the alternative for these patients with juxtarenal or pararenal aortic aneurysm is open surgical repair. The open surgical concurrent control group enrolled in the original Endologix trial between 2000 and 2003 (that served as the basis for approval of the bifurcated stent graft under P040002) consisted of patients with aneurysms of these types. Of the 66 control patients enrolled in that trial, 3.0% had a suprarenal aneurysm, 21% had a pararenal aneurysm, and the remaining patients (76%) had a juxtarenal aneurysm or infrarenal aneurysm unsuitable for endovascular repair with the Endologix bifurcated device. These patients have completed full five year follow-up as documented in the Endologix PMA final report approved by FDA in 2009 (P040002/R008).

Owing to the availability of patient-level data within the Endologix PMA P040002 for this historical surgical control group with more complex aneurysms as intended to be enrolled in this trial, it is reasonable to consider it for sample size generation for the safety endpoint. The MAE incidence at 30 days in the original PMA trial for the test group and this surgical control group is tabulated below:

¹⁷Fleiss, J. The statistical basis of meta-analysis. *Statistical Methods in Medical Research* 1993;2:121-45.

30-Day MAE Rates in the Endologix PMA Trial (P040002)

Event	Powerlink Test (N=192)	Surgical Control (N=66)
Patients with ≥ 1 MAE	16 (8.3%)	44 (67%)
All-Cause Mortality	2 (1.0%)	4 (6.1%)
Bowel Ischemia	0	6 (9.1%)
Myocardial Infarction	3 (1.5%)	5 (7.6%)
Paraplegia	0	0
Renal Failure	2 (1.0%)	6 (9.1%)
Respiratory Failure	2 (1.0%)	5 (7.6%)
Stroke	0	1 (1.5%)
Blood Loss $\geq 1,000$ cc	11 (5.7%)	38 (58%)

Thus, the 30-day MAE rates were 8.3% (endovascular test group) and 67% (surgical control group). To be conservative and to account for the fact that in the present trial, only more complex juxtarenal or pararenal aneurysms will be treated endovascularly, the rate for the test arm has been increased to 16.6%. It is expected that the rate of MAEs within 30 days in the treatment group in this trial will be smaller than that of the historical surgical control group as noted above. The sample size for this trial is calculated by considering this a superiority trial.

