Similar to the strategy employed above, to determine those factors that may be associated with MAE, a supportive covariate analyses will be performed by logistic regression to determine if there are differences in the rates among groups when adjusted for other factors in the test group only. Covariates for these analyses will be age, gender, ASA class, cardiac/coronary artery disease (a composite variable to include arrhythmia, CHF, prior MI, CABG/PCI, heart valve repair/replacement), histories of cancer, cerebrovascular disease, coagulopathy, COPD, diabetes, hypertension, liver disease, peripheral arterial occlusive disease, renal failure, smoking, maximum aneurysm diameter, and study site. The final model will be reduced by backward elimination until no covariate terms remain in the model with a P-value less than 0.05.

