To determine those factors that may be associated with Treatment Success, covariate analyses will be performed by logistic regression to determine if there are differences in the Treatment Success rates in the Test group when adjusted for other factors. Possible covariates eligible for these analyses will be age, gender, ASA class, cardiac/coronary artery disease (a composite variable to include arrhythmia, CHF, prior MI, CABG/PCI, heart valve repair/replacement), cancer, cerebrovascular disease, COPD, diabetes, hypertension, liver disease, peripheral arterial occlusive disease, renal failure, smoking, maximum aneurysm diameter, and study site. Because there are too many possible covariates to include in a model, screening is necessary to reduce the number of eligible covariates for consideration in the final model. Screening logistic regression models to include only the covariate, will be used. If the P-value for the screening model for the covariate is less than 0.20, the covariate will be included in the competition for the final model. The final model will be obtained by manual backward elimination to have the seven or fewer covariates with P-value less than 0.05.

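### The test-group MAE model starts at about 0.4 to 0.8 expected events per parameter, the Treatment Success model allows about 1.2 to 1.4 failures per covariate, and neither has a sparse-data rule

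*Combined protocol and SAP*

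**What the plan says.** For both primary endpoints the synopsis states: "Multivariable analyses will be used to assess predictors of trial success".

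The performance-goal part of section 10.6.4 describes the MAE model in the test group only. It names 15 covariates: age, gender, ASA class, the cardiac composite, ten histories or conditions, and aneurysm diameter. It then adds site and goes straight to elimination: "maximum aneurysm diameter, and study site. The final model will be reduced by backward elimination". There is no screening step. Earlier in 10.6.4, alongside the comparison with the surgical controls, a second test-only model is planned to see whether site still matters once covariates are included.

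Section 10.7.3 has almost the same list for Treatment Success (14 covariates, without coagulopathy, plus site), but treats it differently: "Because there are too many possible covariates to include in a model, screening is necessary". Each candidate is screened univariably at P < 0.20, and then "The final model will be obtained by manual backward elimination to have the seven or fewer covariates with P-value less than 0.05".

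Neither section sets a limit on parameters relative to events, provides for a penalised or exact fit, or says what happens if a fit does not converge.

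**The concern.** In logistic regression the information comes mainly from the rarer outcome. When parameters outnumber events, some combination of covariates often predicts the outcome perfectly for some patients (separation). The affected maximum-likelihood coefficients then run to infinity and their Wald P-values mean little. Backward elimination uses those P-values to decide what to drop, so a bad starting fit can steer the whole path.

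The plan sees this problem for Treatment Success but not for MAE, although the lists are nearly identical and the patients are the same. What is at stake is the list of predictors promised in the synopsis and the statement on whether site influences the MAE rate. With zero-event sites, a finding that site is no longer significant could be an artefact of the fit.

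**Working it through.** **Inputs**
- Trial Phase patients: 97 (section 5.1: "During the Trial Phase, 97 patients are planned to be enrolled at the investigational sites").
- Sites: at most 25 (section 5.1: "Up to 25 sites and up to 122 patients will participate in this trial").
- Fewest sites: section 4.3 says "An investigational site may not enroll more than 20% of the total Trial Phase enrollment". 0.20 × 97 = 19.4, so at most 19 per site; 5 × 19 = 95 < 97, so at least 6 sites.
- MAE rate: 16.6% (section 10.6.2: "the rate for the test arm has been increased to 16.6").
- Treatment Success: 82 evaluable of 97 recruited, 90% success (section 10.7.2).
- Covariate prevalences: not given; assumed below.

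**The plan's own figures reproduce.** Exact binomial, n = 82, 0.80 against 0.90, one-sided 0.05: reject at 72 or more successes, actual alpha 0.0458, power 0.8057 (stated 80.58%). 82/0.85 = 96.5, so 97. Safety, 97 against 66 patients at 0.434 against 0.670: one-sided Fisher power 0.810 (stated 81%).

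**MAE events per parameter.** Expected events = 97 × 0.166 = 16.1. Counting one parameter per covariate (fewer than needed if ASA class is categorical) and (sites − 1) for site:

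| Layout | Parameters | Events per parameter |
|---|---|---|
| 25 sites | 15 + 24 = 39 | 16.1/39 = 0.41 |
| 6 sites | 15 + 5 = 20 | 16.1/20 = 0.81 |
| no site term | 15 | 16.1/15 = 1.07 |

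Even at 0.434, the highest MAE rate for which 10.6.2 quotes power, 25 sites give 97 × 0.434 / 39 = 42.1/39 = 1.08.

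**Zero-event sites.** Sixteen patients with events can occupy at most 16 sites. With 25 enrolling sites, 25 − 16 = 9 or more have none, and their coefficients diverge.

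**Separation in simulated data** (n = 97, 16.6% MAE, outcome unrelated to covariates, linear-programming check; assumed prevalences 5–80% or 15–80%):

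| Layout | Trials with some separation |
|---|---|
| 25 sites, unpooled | 100% |
| 25 sites with small-site pooling, or 10 sites | about 90–99% |
| 6 sites | 61–84% |
| no site term | 15–74% |

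The shares fall at higher MAE rates. At 0.434 with prevalences 15–80% they were 0% without site, 2% with 6 sites, 12% with 10 and 100% with 25.

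**Treatment Success.** Failures at 90% success: 82 × 0.10 = 8.2, or 97 × 0.10 = 9.7. Divided by seven: 1.17 to 1.39 per covariate. At 80% success: 16.4 to 19.4 failures, or 2.3 to 2.8 per covariate.

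**False predictors.** The 10.7.3 rule was simulated with 14 unrelated covariates, 82 or 97 patients and 10% failures. At least one covariate survived in about 58–65% of trials when likelihood-ratio tests were used and about 30–40% with Wald tests. Section 10.7.3 does not name the test. For comparison, 14 independent tests at 0.05 give 1 − 0.95^14 = 51% whatever the event count.

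**The case against.** A reader might infer that the MAE model has no finite estimates and cannot be fitted by maximum likelihood at all. The documents do not support that. Twenty-five is a maximum, 6 sites are permitted, and section 10.4 describes merging small sites, generally those with four or fewer patients; at 25 sites the mean is 97/25 = 3.9. Separation is also usually partial: coefficients for empty sites and rare conditions diverge while others can stay finite. In simulations that also included rarer covariates (prevalences 2–80%), complete separation occurred in under 5% of trials with 10 or fewer sites, against 20–49% with 25 unpooled sites. Away from 25 sites the percentages depend heavily on assumed prevalences. This objection stands, and it limits the claim. It does not remove it: the 10.4 merger is written for the comparability analysis and yields one pseudo-site no larger than the largest site, and separation stayed frequent after pooling.

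A reader might also infer that the Treatment Success model will mostly report noise because it is overfitted. That goes too far as well. Seven is a ceiling reached after screening and elimination, the error rate depends on the unnamed test, much of it is multiplicity that any exploratory search carries, and the simulation assumes that no covariate matters.

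Finally, 10.6.4 calls the MAE model supportive and places it in the performance-goal fallback. That is right and bears on severity. The site model earlier in 10.6.4 faces the same sparse events, however, so the difficulty is not confined to the fallback, although no elimination rule is set there.

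**Conclusion.** The point holds in a limited form. At the planned MAE rate, elimination starts from a fit with about 0.4 to 0.8 events per parameter. Non-finite site coefficients are certain with 25 unpooled sites. With fewer or pooled sites, some separation is likely but not guaranteed. The Treatment Success ceiling is too high for 8 to 10 failures, and success above 90%, which section 10.7.2 expects, would leave fewer still.

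The counts rest on the plan's own numbers. The separation and false-predictor percentages rest on assumed prevalences and no true effects, and should be read as ranges. Neither primary test, nor any decision on trial success, depends on these models. The change is worth making because the synopsis promises the predictors for both endpoints, but it is not critical.

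**What to change.** In both covariate analyses (10.6.4 and 10.7.3) and in the test-only site model of 10.6.4:

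- Limit the multivariable model to a few covariates chosen in advance. At an assumed 5 to 10 events per parameter, 16 events support about 1 to 3 for MAE, and 8 to 10 failures about 1 to 2 for Treatment Success.
- Fit by Firth-penalised logistic regression.
- Enter site as a random intercept, or with small sites grouped as in 10.4, and say that the grouping applies here.
- Report the remaining covariates as univariable odds ratios with intervals, labelled exploratory and unadjusted for multiplicity.

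If any elimination is kept, name the test. The 10.6.4 stopping rule should be corrected at the same time: as worded, it removes the terms with P below 0.05 instead of keeping them.

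The cost is SAP wording and fewer adjusted predictors in the report. The univariable estimates remain open to chance findings, which is why the label matters.

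### The stopping rule for the test-group-only MAE covariate model in section 10.6.4 is reversed, so no term with P below 0.05 can stay in that supportive model

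*Combined protocol and SAP*

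**What the plan says.** After the exact test and the site-weighted test against the 56% performance goal, section 10.6.4 describes a covariate analysis. Its purpose is given as "to determine those factors that may be associated with MAE, a supportive covariate analyses will be performed by logistic regression", and its scope as differences in rates "when adjusted for other factors in the test group only". Sixteen candidate covariates are listed, the last being study site. The reduction rule is: "The final model will be reduced by backward elimination until no covariate terms remain in the model with a P-value less than 0.05".

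Section 10.7.3 describes the corresponding model for Treatment Success. Covariates are first screened one at a time, and those with small P-values go forward: "If the P-value for the screening model for the covariate is less than 0.20, the covariate will be included in the competition for the final" (quote cut short here). The reduction rule that comes after the screening is: "The final model will be obtained by manual backward elimination to have the seven or fewer covariates with P-value less than 0.05".

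The synopsis, under the safety criterion for trial success, also commits to multivariable analyses of predictors of trial success.

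**The concern.** Backward elimination that looks for predictors removes terms with large P-values and stops when only terms below the retention level are left. The section 10.6.4 sentence states the opposite end point: the process is finished when nothing below 0.05 is left. A covariate that is clearly associated with MAE is then, by rule, a reason to go on eliminating.

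At stake is whether this analysis can answer its own question. Section 11.1 makes the independent biostatistician responsible for conducting and reporting the analysis per the plan. Following the sentence gives a final model with no identified factor. Ignoring it is a sensible departure, but one made after the fact on a rule that should have been fixed in advance. The elimination rule is also the only stated means of reducing this model, because section 10.6.4 has no screening step like the one in section 10.7.3.

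**Working it through.** No sample size, power or alpha in the plan rests on this rule, so there is no stated figure to reproduce. The check compares the texts and then illustrates the effect.

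**Comparison of the texts**

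| | MAE model, test group (10.6.4) | Treatment Success model (10.7.3) |
|---|---|---|
| Aim | Find factors associated with MAE | Find factors associated with Treatment Success |
| Screening | None stated | Single-covariate P<0.20 goes forward |
| Method | Backward elimination | Manual backward elimination |
| End point | No term left with P<0.05 | Seven or fewer terms, each with P<0.05 |

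The aims match and the method has the same name, but the end points are opposite. Nothing elsewhere in the document corrects the 10.6.4 sentence.

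**What the literal rule leaves**

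Let M be the set of terms in the current model. The rule says to continue while min P over M is below 0.05, and to stop when min P over M is at least 0.05 or M is empty. Whatever is dropped at each step, the final model therefore has no term with P<0.05. What else it contains depends on the order of removal, which the sentence does not give:

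- Smallest P dropped first: the significant terms go and the non-significant ones stay.
- Largest P dropped first (the usual order): the non-significant terms go first. Elimination must then continue, because significant terms remain, and usually nothing is left.

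**Illustration**

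From the documents: n = 97 ("During the Trial Phase, 97 patients are planned to be enrolled at the investigational sites", section 5.1). Assumed: 8 independent normal covariates, 2 true predictors with log odds ratio 1.2 per SD, 6 null covariates, a mean event rate of about 20%, and 400 runs. The event rate is somewhat above the plan's own assumption for the test arm (section 10.6.2: "the rate for the test arm has been increased to 16.6" per cent).

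| Rule | True predictors kept | Null covariates kept | Mean terms in final model | Mean terms with P<0.05 | Empty model |
|---|---|---|---|---|---|
| Usual: drop largest P until all P<0.05 | 95% | 5% | 2.2 | 2.2 | 0.25% |
| Literal stop, smallest P dropped first | 8% | 96% | 5.9 | 0 | 0% |
| Literal stop, largest P dropped first | 0.75% | 0.3% | 0.03 | 0 | 99% |

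The zeros in the fifth column follow from the rule itself. The other percentages depend on the assumed settings.

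**Information available to the real model**

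At the plan's assumed rate, 97 × 0.166 ≈ 16 patients with an MAE, against 16 listed covariates, one of which (study site) may have up to 25 levels.

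**The case against.** The strongest reply is that this is an obvious slip that nobody would follow. The aim in the same paragraph, the name of the method and the rule in section 10.7.3 all point to one intended meaning. That is very probably right about intent. It does not make the sentence harmless, because the plan is the reference for the analyst. Nor is this the only directional error in the section: 10.7.3 rejects the effectiveness null when z is below 1.645, although the alternative is a success rate above 0.80. Directional wording in section 10 cannot simply be assumed correct.

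A second reply is that little is lost, because about 16 events cannot support 16 covariates whichever way the rule runs. This stands as a limit on the benefit: correcting the phrase will not by itself make the model dependable. It is not a reason to leave the rule reversed.

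Two stronger readings are tempting, and the documents do not support either.

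- A reader might infer that predictors of MAE, including study site, could never be reported. Section 10.6.4 separately plans a test-versus-control logistic model with nearly the same covariates and no elimination rule. It also plans a test-patient multivariable analysis aimed specifically at study site. Section 10.5 tests site homogeneity of the MAE rate by logistic regression, and section 10.8.1 adds an exploratory MAE model if balance fails. None of these carries the reversed rule.
- A reader might infer that the final model necessarily keeps the non-significant covariates. That holds if the significant terms are the ones dropped. In the usual order of removal, the typical result is an empty model.

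**Conclusion.** The stopping rule is wrong as written. Applied literally, it guarantees that no term with P<0.05 stays in the final model, which is therefore empty or holds only non-significant terms. That contradicts the model's stated purpose and the retention rule in section 10.7.3. This conclusion needs no numerical assumption; the simulation percentages are illustrative only.

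The reach is narrow. The model is labelled supportive, covers the test group only, and accompanies the performance-goal analysis that becomes primary only if the propensity-score comparison with the surgical control is abandoned. The primary safety test, its one-sided 0.025 level, the power statements, the 97 patients and the 56% goal are all unaffected. It should be corrected, but it does not put any success decision at risk.

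**What to change.** In the last sentence of section 10.6.4, replace the stopping condition so that backward elimination continues *until all covariate terms remaining in the model have a P-value less than 0.05*, in line with section 10.7.3. It would help to add that the term with the largest P-value is removed at each step, since the order is not stated.

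The cost is one phrase in the analysis plan. No design parameter, data collection or other analysis changes. Given about 16 expected events, the sponsor may also wish to apply the screening step and covariate limit of section 10.7.3 to this model, but that is optional and separate from the correction.
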